4.3 Exclusion Criteria

1. Presence of any significant acute or chronic, uncontrolled medical/psychiatric illness
2. Hepatitis C virus (HCV) antibody positive.
3. HIV antibody positive
4. History or evidence of autoimmune disease or known immunodeficiency of any cause
5. Prolonged therapy with immunomodulators (e.g. corticosteroids) or biologics (e.g. monoclonal antibodies, IFN) within 3 months of screening
6. Receipt of immunoglobulin or other blood products within 3 months prior to screening
7. Receipt of any investigational drug or vaccine within 3 months prior to screening
8. Cohorts 1-4: Receipt of any adenoviral vaccine within 3 months prior to administration of ChAdOx1-HBV on Day 0, or plan to receive an adenoviral-based vaccine within 3 months after Day 0

Cohorts 5 and 6: Receipt of any adenoviral vaccine (other than AZD1222 per inclusion criterion 13) within 3 months prior to administration of ChAdOx1-HBV on Day 0, or plan to receive an adenoviral-based vaccine within 3 months after Day 0

9. Receipt of any live vaccines within 30 days prior to screening
10. Receipt of any inactivated vaccines within 14 days prior to screening
11. History of allergic disease or reactions likely to be exacerbated by any component of the vaccine
12. Any history of anaphylaxis in reaction to vaccination
13. Malignancy within 5 years prior to screening with the exception of specific cancers that are cured by surgical resection (e.g. except basal cell skin carcinoma of the skin and cervical carcinoma). Participants under evaluation for possible malignancy are not eligible
14. Current alcohol or substance abuse judged by the Investigator to potentially interfere with participant safety and compliance
15. Significant cardiac disease or unstable uncontrolled cardiac disease
16. Any laboratory test at screening which is abnormal and which is deemed by the Investigator to be clinically significant
17. Any other finding that, in the opinion of the Investigator, deems the participant unsuitable for the study

Additionally, for healthy participants (cohorts 1, 2, 5 and 6)

18. HBsAg positive

Additionally, for participants with well controlled CHB (cohorts 3 and 4)

19. Co-infection with hepatitis delta
20. Documented cirrhosis or advanced fibrosis indicated by a liver biopsy within 6 months prior to screening.

In the absence of an appropriate liver biopsy, either 1 of the following:

- Screening Fibroscan with a result >9 kPa within ≤ 6 months of screening or
- Screening FibroTest >0.48 and AST to platelet ratio index of >1

In the event of discordant results between non-invasive methods, the Fibroscan result will take precedence.

21. ALT $>3 \times$ ULN, INR >1.5 unless the participant was stable on an anticoagulant regimen affecting INR, albumin <35 g/L, total bilirubin >34.2 μ mol/L, platelet count $<100 \times 10^9$ /L
22. A history of liver decompensation (e.g. ascites, encephalopathy or variceal haemorrhage)
23. Prior or current hepatocellular carcinoma
24. Chronic liver disease of a non-HBV aetiology
25. Any herbal supplements and or other medicines with potential liver toxicity within the previous 3 months prior to enrolment into this study

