To support this interval, this study aims to produce data of the response in healthy volunteers to our ChAdOx-1 HBV vaccine following the use of the AZD1222 vaccine. T cell responses (the critical immunological factor in chronic HBV infection) will be compared in participants who have received either a prior two-dose series of AZD1222 with those who have received at least two prior doses of either the Pfizer mRNA COVID 19 vaccine (Comirnaty) or the Moderna COVID-19 vaccine (Spikevax). Due to the recommendation to use the AZD1222 in those over the age of 40 years, we will confine our study to 40-60 years of age and keep the interval from the latest COVID-19 vaccine to a narrow window of 10-18 weeks. No interference on HBV -focused T cell responses is expected from either the Pfizer vaccine or the Moderna vaccine, so the interval from the latest COVID-19 vaccine will be between 6 to 30 weeks

2

STUDY OBJECTIVES AND ENDPOINTS

Objectives	Endpoints
Primary	Primary
Determine the safety and tolerability of different doses of a single vaccination of ChAdOx1-HBV in healthy participants and in participants with CHB infection and virally suppressed with oral antiviral medication.	Incidence of safety and reactogenicity events: 
 • Adverse events and/or adverse events leading to study discontinuation • Serious adverse events • Grade ≥ 3 local and systemic reactions
Secondary	Secondary

 • Determine the immunogenicity of ChAdOx1-HBV in (A) healthy participants and in (B) participants with CHB, virally suppressed with oral antiviral medication 
Determine the effect of ChAdOx1-HBV on the level of HBsAg in participants with CHB infection, virally suppressed with oral antiviral medication
	
 • A multi-parameter index made of CD4+ magnitude, CD4+ avidity, and CD8+ magnitude • Mean reduction in HbsAg titre at Day 84 and Day 168 post-vaccination (last visit) • Proportion of CHB participants with HbeAg and HbsAg loss • Proportion of CHB participants with HbeAg and HbsAg seroconversion • Reduction of hepatitis B DNA levels • Total T cell response to the antigens encoded by ChAdOx1-HBV as measured in a peptide-stimulated ELISpot assay
Exploratory	Exploratory

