3.1.2 *Study Methodology*

Participants will be screened in the period Day -42 to Day -1. Informed consent will be obtained before any study specific procedures are performed. Eligible participants will then attend the clinic to receive study vaccine on Day 0. Participants will be enrolled sequentially.

The study will investigate response to study vaccine as shown in [Table 2](#). On Day 0, an electronic diary (eDiary), tape measure and thermometer will be provided to perform self-assessment of local and systemic reactogenicity. All participants will then have a follow-up telephone call on Day 1 and return to the clinic for study assessments on Days 7, 14, 28, 84. Participants in cohorts 1-4 only, will also have follow up visits on Day 56 and Day 168. End of study visit procedures will be performed at the final visit.

Five healthy participants will be administered the low dose first (cohort 1). Dose escalation will only be initiated in the next 5 healthy participants (cohort 2) following SMC review.

Six CHB participants will be administered the low dose (cohort 3) before the dose escalation is initiated in the remaining 6 CHB participants (cohort 4).

Thirty healthy participants (15 who have received two doses of AZD1222 [cohort 5] and 15 who have received at least two doses of either Pfizer or Moderna mRNA COVID-19 vaccine [cohort 6]) will be dosed in parallel with the high dose used in cohorts 2 and 4.

The first participant in each of cohorts 1-4 will be assessed for 1 hour in the clinic post-vaccination in case of immediate adverse events (timed after the end of study vaccine administration). All other participants will be assessed for 30 minutes.

The safety and immunogenicity assessments to be performed in cohorts 1-4 are:

- Haematology (full blood count, haemoglobin, haematocrit, erythrocytes, mean cell volume, mean corpuscular haemoglobin, mean corpuscular haemoglobin concentration, leukocytes, neutrophils, lymphocytes, monocytes, eosinophils, basophils, fibrinogen, prothrombin time [PT] and international normalised ratio [INR], activated partial thromboplastin time [aPTT] and platelets) will be analysed at screening, pre-vaccination on Day 0 and on Days 7, 14, 28, 56, 84 and 168
- Biochemistry (sodium, potassium, urea, creatinine and albumin) will be analysed at screening, pre-vaccination on Day 0 and on Days 7, 14, 28, 56, 84 and 168

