3.3 Benefit Risk Assessment

There are potential known and unknown risks associated with vaccination. With any vaccine, including those that are licensed, there is a rare risk of anaphylaxis which can be fatal. All participants will be observed in the clinic for at least 30 minutes post-vaccination.

Intramuscular injection of vaccines frequently causes the local and systemic signs and symptoms that are being collected as adverse events. These will be solicited from the participant to ensure they are not occurring more frequently or are more severe than expected based on previous experience with the same or similar viral vectors.

With any new treatment there is always a possibility of an unexpected adverse events.

The administration of ChAdOx1-HBV in this study may interfere with the effectiveness of other vaccines subsequently administered to the participant. The ChAdOx1 vector induces anti-vector immunity in addition to an antigen-specific immune response. Of particular concern are neutralising antibodies directed against the capsid structure of the vector, which may have a negative effect on subsequent immunisations with the same or related adenoviral vector by neutralising the vector before it has a chance to transduce target cells. This effect decreases with longer interval between the vaccines [28,29]. In particular, there is a concern that the ChAdOx1-HBV administered in this study could decrease the response to the AstraZeneca COVID-19 vaccine, which has the same viral vector, especially if it is administered within 3 months of ChAdOx1-HBV. The Janssen (Johnson & Johnson) COVID-19 vaccine is also made with an adenovirus, and some interference cannot be ruled out. Therefore, it is recommended that participants in this study receive an alternative type of COVID-19 vaccine, such as an mRNA or protein vaccine, at least 2 weeks before and after ChAdOx1-HBV in this study.

There are also routinely scheduled reviews of safety and efficacy data throughout the study by the SMC. Stopping and holding rules have been defined for the study (see [Section 3.1.3](#)) and a DMC will perform a review of safety data if one of these is met.

Although this is the first time ChAdOx1-HBV has been administered to humans, the ChAdOx1 vector has been widely administered for many pathologies without significant safety concerns (see [Section 1.4](#)). Further detail is provided in the Investigator's Brochure.

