6 STUDY PROCEDURES AT EACH VISIT/SCHEDULE OF ASSESSMENTS

The study consists of the following:

- A 42-day screening period before the start of the study period
- A study period of 168 days, consisting of a vaccination day on Day 0, a follow-up telephone call on Day 1 and follow-up visits on Days 7, 14, 28, 56. Participants in cohorts 1-4 only, will also have follow up visits on Day 56 and Day 168. End of study visit procedures will be performed at the final visit.

The schedule of assessments at each visit is shown in [Table 2](#) and listed in [Section 6.1](#) to [Section 6.4](#). The study assessments are described in [Section 7](#).

Note: any additional visits or assessments performed during the study e.g. to assess adverse events must also be recorded on the unscheduled procedures or unscheduled visits in the eCRF.

Table 2 Overall Schedule of Assessments at Each Study Visit

Visit/Call	Screen	Vaccination			Follow-up						End of Study	
	Timepoint	Day -42 to -1		Day 0	Day 1	Day 7±1	Day 14±1	Day 28±2	Day 56±3 (cohorts 1-4)	Day 84±7[a]		
		Pre-	0	Post-								
Informed consent		X										
Baseline/eligibility variables												
Demographics		X										
Inclusion and exclusion criteria		X	X									
Height and Weight		X										
Medical and disease history		X	X									
HIV Ab, HCV Ab, HBsAg, HDV Ab[b]		X										
Urinalysis		X										
Urine pregnancy test (β -hCG) [c]		X	X						X	X	X	
Laboratory eligibility and safety tests												
Haematology [d]		X	X			X	X	X	X	X	X	
Biochemistry[d]		X	X			X	X	X	X	X	X	
Liver function tests[e]		X	X			X	X	X	X	X	X	
Study vaccination												
Vaccination				X								
Post-vaccination observation[f]					X							
Other Safety assessments												
Full physical examination		X	X									
Directed physical examination if required						X	X	X	X	X	X	
Vital signs[g]		X	X		X		X	X	X	X	X	
Local/systemic reactogenicity [h]			X		X	X						
Unsolicited adverse events [i]		X	X	X	X	X	X	X				
Serious adverse events and adverse events of special interest		X	X	X	X	X	X	X	X	X	X	
Prior and concomitant medications		X	X	X	X	X	X	X	X	X	X	
Blood for HBV disease markers												
Healthy participants (HBsAb, HBcAb)			X								X[j]	
CHB (HBV DNA, HBsAg quantitative)		X	X						X	X	X	

Visit/Call	Screen	Vaccination			Follow-up						End of Study	
		Day -42 to -1		Day 0		Day 1	Day 7±1	Day 14±1	Day 28±2	Day 56±3 (cohorts 1-4)	Day 84±7[a]	
		Pre-	0	Post-								
CHB (HBeAg, anti-HBe, anti-HBs, pgRNA, HBcAg, anti-HBc)		X							X	X	X	X

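### Exclusions 6, 7, 9 and 10 end their washouts at screening, not Day 0, so no firm rule covers non-adenoviral vaccines, blood products or investigational agents in the up to 42 days before dosing

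*Protocol*

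**What the plan says.** Numbers here follow Protocol Section 4.3. The synopsis splits exclusion 8 in two, so its live and inactivated vaccine criteria are 10 and 11.

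- Exclusion 6: "Receipt of immunoglobulin or other blood products within 3 months prior to screening". Exclusion 7 applies the same 3-month look-back from screening to investigational drugs and vaccines.
- Exclusion 9 bars live vaccines in the 30 days before screening. Exclusion 10 bars "Receipt of any inactivated vaccines within 14 days prior to screening".
- Exclusion 5 is worded differently: "Prolonged therapy with immunomodulators (e.g. corticosteroids) or biologics (e.g. monoclonal antibodies, IFN) within 3 months of screening".
- Exclusion 8 uses another anchor: "Receipt of any adenoviral vaccine within 3 months prior to administration of ChAdOx1-HBV on Day 0". For cohorts 5 and 6 it exempts AZD1222 given under inclusion criterion 13.
- Timing, Section 3.1.2: "Participants will be screened in the period Day -42 to Day -1". Section 6 agrees: "A 42-day screening period before the start of the study period".

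Sections 5.8.2.1 and 6.2 require eligibility to be re-confirmed on Day 0. Section 4.3.1.1 defers dosing only for acute disease or raised temperature. Section 5.9 records other vaccines and medications and prohibits none. Section 3.3 recommends that any COVID-19 vaccine be of a non-adenoviral type, "such as an mRNA or protein vaccine, at least 2 weeks before and after ChAdOx1-HBV in this study".

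**The concern.** A washout protects the data only if it ends at dosing. Here most of them end at a visit that can be six weeks earlier, and the Day 0 re-check applies the same screening-anchored wording. A participant who has another vaccine after screening still meets the criteria as written.

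Three things are at stake.

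- **Safety.** The primary endpoints are adverse events, serious adverse events and Grade 3 or higher local and systemic reactions. SAP 10.8.2 summarises the worst post-vaccination grade of each reaction with no adjustment for the pre-dose assessment. SAP 10.8.1 treats any event starting on or after the vaccination date as treatment-emergent. A recent vaccine could plausibly add fever, myalgia, fatigue or headache to those counts. Under Section 8.1.4 a severe reaction also prompts immediate review by the Safety Monitoring Committee.
- **Immunogenicity.** A recent vaccine or immunoglobulin could shift the T cell response, including in the cohort 5 versus cohort 6 comparison, whose purpose is to isolate the effect of an earlier vaccine.
- **Visibility.** Because no criterion is breached, no eligibility deviation arises. The participant stays in the per-protocol and immunogenicity sets (SAP 9.2, 9.3) unless the data review meeting decides otherwise. SAP 10.5 would class a vaccine given before Day 0 as prior medication, which is listed but not tabulated.

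**Working it through.** **Inputs.** Screening day s lies between -42 and -1 (Sections 3.1.2 and 6). Washout lengths W are 14 days (exclusion 10), 30 days (exclusion 9) and 3 months (exclusions 6 and 7). I take 3 months as 91 days; the range for three calendar months is 89 to 92.

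**The plan's own figure.** Day -42 to Day -1 inclusive is 42 days, which matches the stated screening period.

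**Formula.** Counting back from screening, the excluded days run from s - W to s - 1. A Day 0 washout of the same length would cover Days -W to -1. The part of that period left uncovered is min(W, |s|) days.

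| Screening day | Inactivated, W = 14 | Live, W = 30 | 3 months, W = 91 |
|---|---|---|---|
| -42 | excludes -56 to -43; 14 of 14 uncovered | excludes -72 to -43; 30 of 30 uncovered | excludes -133 to -43; 42 of 91 uncovered |
| -14 | excludes -28 to -15; 14 of 14 uncovered | excludes -44 to -15; 14 of 30 uncovered | excludes -105 to -15; 14 of 91 uncovered |
| -1 | excludes -15 to -2; 1 of 14 uncovered | excludes -31 to -2; 1 of 30 uncovered | excludes -92 to -2; 1 of 91 uncovered |

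The last excluded day is s - 1, so it is never later than Day -2. Day -1 is outside exclusions 6, 7, 9 and 10 whatever the screening date. The 91-day assumption changes only the denominator: 42 days are uncovered for any value from 89 to 92.

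**Weight of one participant.** 1/6 = 17% in cohort 3 or 4; 1/15 = 6.7% in cohort 5 or 6.

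**COVID-19 vaccine passages, side by side.**

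- Section 1.5.1 says the study will "keep the interval from the latest COVID-19 vaccine to a narrow window of 10-18 weeks". Criterion 13 ties 10 to 18 weeks to the second AZD1222 dose instead, and says nothing of a later dose of another type.
- Criteria 13 and 16 count to enrolment, while the secondary objective counts 10 to 18 weeks to ChAdOx1-HBV. Section 4.1 equates enrolment with informed consent. If consent is given on Day -42, a second AZD1222 dose 18 weeks before enrolment is 18 + 42/7 = 24 weeks before dosing.
- Section 3.3 states a 2-week spacing, as a recommendation only.

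These passages do not give a single rule.

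**The case against.** The strongest reply is that the protocol is not defenceless. Criteria 6, 11 and 14 require healthy participants to have no current condition that may influence results, and exclusion 17 lets the investigator reject anyone for any other finding. Both fall under the Day 0 re-check. Reactogenicity is assessed before dosing and listed, events with an earlier onset date are pre-treatment, and causality assessment must weigh alternative causes. Moderate or severe illness, or temperature above 38°C, is a contraindication to dosing. This stands as mitigation. But the criteria are discretionary, and the worst post-vaccination grade is still what is tabulated. Solicited site reactions are deemed related by rule (Section 8.2.3.2).

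A reader might infer more than the documents support:

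- **That anyone vaccinated the day before dosing is eligible.** Not for adenoviral vaccines: exclusion 8 is tied to Day 0.
- **That exclusion 5 plainly stops at screening.** Its wording can run in both directions, and it covers only prolonged therapy. A short steroid course is not excluded under any anchor.
- **That cohort 5 openly admits recent mRNA boosters while cohort 6 guarantees six weeks before dosing.** Cohort 5 is described as having had two AZD1222 doses, against at least two mRNA doses in cohort 6, so a boosted person is arguably outside its description. The third-dose columns in SAP Listing 16.2.12 do not show cohort 5 boosters, since the amendment allowing more than two doses changed criterion 16. Criterion 16 itself counts to enrolment, so cohort 6 has a similar gap after consent.
- **That one case would be 20% of a cohort.** That is 1/5 in cohort 1 or 2, whose enrolment was complete before cohorts 5 and 6 were added (Section 5.7). Rewording cannot change those data.
- **That 42 days is a period of reactogenicity risk.** It is calendar time without a rule. The documents give no duration for reactions to other vaccines.

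**Conclusion.** The point holds for exclusions 6, 7, 9 and 10. As written, they leave between 1 and 42 days before dosing without a firm rule for non-adenoviral live or inactivated vaccines, blood products and investigational agents. With screening on Day -42, the 14-day and 30-day washouts protect none of the days they appear meant to protect. Exclusion 5 is ambiguous rather than wrong.

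The conclusion assumes the criteria are read literally. Sites may in practice have used discretion, and the documents do not show how many participants, if any, were exposed. The possible effect on reactions and T cell responses is plausible but not quantified. No sample size or power figure is affected. The change is worth making because the cohorts are small and exclusion 8 already supplies the needed wording.

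**What to change.** 1. In exclusions 6, 7, 9 and 10, and for clarity in 5, keep the existing lengths and count them back from administration of study vaccine on Day 0, as exclusion 8 does. Make the same change in the synopsis and apply it at the Day 0 re-check. If the look-back from screening has a purpose of its own, keep it alongside the Day 0 limit, because re-anchoring alone would also release some exposures before screening that are now excluded.
2. Reconcile four items: the Section 3.3 recommendation, the latest-vaccine wording in Section 1.5.1, criterion 13, and the enrolment anchor in criteria 13 and 16. This review does not choose an interval.
3. For participants already dosed, use SAP Listings 16.2.4.6 and 16.2.12 to identify anything received between screening and Day 0. Review it at the data review meeting when the analysis sets are settled.

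The cost is wording in five criteria and the synopsis, plus a check of listings already planned. A few Day 0 visits may have to move. No new procedure is needed.

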4.3.1 Removal of Participants from Vaccination or Assessment

4.3.1.1 Contraindications to Vaccination

The following events constitute contraindications to administration of study vaccine at that point in time; if any one of these events occurs at the time scheduled for vaccination, the participant may be vaccinated at a later date, or withdrawn from the study at the discretion of the Investigator.

- Acute disease at the time of vaccination. Acute disease is defined as the presence of a moderate or severe illness with or without fever. All study vaccines can be administered to participants with a minor illness such as diarrhoea, mild upper respiratory infection with or without low-grade febrile illness
- Temperature of $>38^{\circ}\text{C}$ (100.4°F) at the time of vaccination

4.3.1.2 Study Discontinuation

Participants may choose to discontinue study assessments by withdrawal of consent. If the participant discontinues from taking the study vaccine but does not withdraw consent, the Investigator or research worker should attempt to continue safety follow-up assessments.

Participants may be withdrawn from the study vaccine, but followed up for safety, in the event of:

- A severe adverse event or SAE
- Difficulties in obtaining blood or other samples
- Failure of the participant to comply with the protocol requirements or to cooperate with the Investigator
- For safety reasons, it being in the best interest of the participant that he/she be withdrawn, in the Investigator's opinion
- A positive pregnancy test or if the participant is non-compliant with the contraception requirements (see [Section 4.2](#))
- Development of a medical condition that requires concomitant treatment with a potentially toxic therapy

Participants must be withdrawn from the study in the event of:

- Withdrawal of consent

4.3.2 Study Termination

The study may be terminated, either at one centre or all centres for the following reasons:

- The discovery of an unexpected, serious or unacceptable risk to participants enrolled in the study
- The decision on the part of the Sponsor to suspend or discontinue testing, evaluation or development of ChAdOx1-HBV. In the event of the Sponsor's decision to no longer supply study vaccine, ample notification will be provided so that appropriate adjustments to treatment can be made

- Serious failure of the Investigator to comply with International Council on Harmonisation of Technical Requirements for Registration of Pharmaceuticals for Human Use (ICH) Good Clinical Practice (GCP) [34] or local regulations
- Submission of knowingly false information from the study centre to the Sponsor, the Health Research Authority (HRA)/ REC or Competent Authorities
- Major and repeated, non-adherence to the protocol

The Sponsor must be informed immediately in the event of any major protocol deviation or serious breach of ICH GCP.

